2.3.3 Known Potential Benefits

Remdesivir may or may not improve the clinical outcome of an individual subject with COVID-19 who participates in this trial. However, there is potential benefit to society from their participation in this study resulting from insights gained about the therapeutic agent under study as well as the natural history of the disease. While there may not be benefits for an individual subject, there may be benefits to society if a safe, efficacious therapeutic agent can be identified during this global COVID-19 outbreak.

2.3.4 Assessment of Potential Risks and Benefits

Remdesivir is generally a well-tolerated medication. There are liver toxicities that have been observed in prior studies. These have been self-limited and resolved after cessation of the medication. There is the potential for renal toxicities as observed in pre-clinical data. By excluding those with elevated liver transaminases and decreased kidney function (eGFR < 30 ml/min or requires hemodialysis or hemofiltration), and appropriate monitoring during the study, we can minimize the risk to subjects. While there may not be benefits for an individual subject, there may be benefits to society if a safe, efficacious therapeutic agent can be identified during this global COVID-19 outbreak. The potential risks therefore are thought to be acceptable given the potential benefits.

3. OBJECTIVES AND ENDPOINTS

The overall objective of the study is to evaluate the clinical efficacy and safety of different investigational therapeutics relative to the control arm among hospitalized adults who have COVID-19.

OBJECTIVES	ENDPOINTS (OUTCOME MEASURES)
Primary	

To evaluate the clinical efficacy, as assessed by time to recovery, of different investigational therapeutics as compared to the control arm.
	
Day of recovery is defined as the first day on which the subject satisfies one of the following three categories from the ordinal scale:
 
 • Hospitalized, not requiring supplemental oxygen - no longer requires ongoing medical care; • Not hospitalized, limitation on activities and/or requiring home oxygen; • Not hospitalized, no limitations on activities. 
Recovery is evaluated up until Day 29.

Key Secondary	

To evaluate the clinical efficacy of different investigational therapeutics relative to the control arm in adults hospitalized with COVID-19 according to clinical status (8-point ordinal scale) at Day 15
	
 • Death; • Hospitalized, on invasive mechanical ventilation or ECMO; • Hospitalized, on non-invasive ventilation or high flow oxygen devices; • Hospitalized, requiring supplemental oxygen; • Hospitalized, not requiring supplemental oxygen - requiring ongoing medical care (COVID-19 related or otherwise); • Hospitalized, not requiring supplemental oxygen - no longer requires ongoing medical care; • Not hospitalized, limitation on activities and/or requiring home oxygen; • Not hospitalized, no limitations on activities.
Additional Secondary	

1. To evaluate the clinical efficacy of different investigational therapeutics as compared to the control arm as assessed by:
 
 • Clinical Severity 
 ○ Ordinal scale: 
 ▪ Time to an improvement of one category and two categories from Day 1 (baseline) using an ordinal scale. 	
 • Clinical outcome assessed using ordinal scale daily while hospitalized and on Days 15, 22, and 29.

OBJECTIVES	ENDPOINTS (OUTCOME MEASURES)

 ▪ Subject clinical status using ordinal scale at Days 3, 5, 8, 11, 15, 22, and 29. ▪ Mean change in the ordinal scale from Day 1 to Days 3, 5, 8, 11, 15, 22, and 29. 	

 ○ National Early Warning Score (NEWS): 
 ▪ Time to discharge or to a NEWS of ≤ 2 and maintained for 24 hours, whichever occurs first. ▪ Change from Day 1 to Days 3, 5, 8, 11, 15, and 29 in NEWS. 	
 • NEWS assessed daily while hospitalized and on Days 15 and 29.

 ○ Oxygenation: 
 ▪ Oxygenation use up to Day 29. ▪ Incidence and duration of new oxygen use during the study. 	
 • Days of supplemental oxygen (if applicable) up to Day 29

 ○ Non-invasive ventilation/high flow oxygen: 
 ▪ Non-invasive ventilation/high flow oxygen use up to Day 29. ▪ Incidence and duration of new non-invasive ventilation or high flow oxygen use during the study. 	
 • Days of non-invasive ventilation/high flow oxygen (if applicable) up to Day 29

 ○ Invasive Mechanical Ventilation / extracorporeal membrane oxygenation (ECMO): 
 ▪ Ventilator / ECMO use up to Day 29. ▪ Incidence and duration of new mechanical ventilation or ECMO use during the study. 	
 • Days of invasive mechanical ventilation/ECMO(if applicable) up to Day 29.

 • Hospitalization 
 ○ Duration of hospitalization (days). 	
 • Days of hospitalization up to Day 29

 • Mortality 
 ○ 14-day mortality ○ 29-day mortality 	
 • Date and cause of death (if applicable)

OBJECTIVES	ENDPOINTS (OUTCOME MEASURES)

2. To evaluate the safety of different investigational therapeutics as compared to the control arm as assessed by:
 
 • Cumulative incidence of SAEs through Day 29. • Cumulative incidence of Grade 3 and 4 clinical and/or laboratory AEs through Day 29. • Discontinuation or temporary suspension of infusions (for any reason) • Changes in white blood cell (WBC) count with differential, hemoglobin, platelets, creatinine, glucose, total bilirubin, alanine aminotransferase (ALT), aspartate aminotransferase (AST), and prothrombin time (PT) over time (analysis of lab values in addition to AEs noted above). 	
 • SAEs • Grade 3 and 4 AEs • WBC with differential, hemoglobin, platelets, creatinine, glucose, total bilirubin, ALT, AST, and PT on Day 1; Days 3, 5, 8, and 11 (while hospitalized); and Days 15 and 29 (if attends in-person visit or still hospitalized).
Exploratory	

To evaluate the virologic efficacy of different investigational therapeutics as compared to the control arm as assessed by:
 
 • Percent of subjects with SARS-CoV-2 detectable in OP sample at Days 3, 5, 8, 11, 15, and 29. • Quantitative SARS-CoV-2 virus in OP sample at Days 3, 5, 8, 11, 15, and 29. • Development of resistance of SARS-CoV-2 in OP sample at Days 3, 5, 8, 11, 15, and 29. • Quantitative SARS-CoV-2 virus in blood at Days 3, 5, 8, and 11. 	
 • Qualitative and quantitative polymerase chain reaction (PCR) for SARS-CoV-2 in OP swab on Day 1; Days 3, 5, 8, and 11 (while hospitalized); and Days 15 and 29 (if attends in-person visit or still hospitalized). • Qualitative and quantitative PCR for SARS-CoV-2 in blood on Day 1; Days 3, 5, 8, and 11 (while hospitalized).

4. STUDY DESIGN

4.1 Overall Design

This study is an adaptive, randomized, double-blind, placebo-controlled trial to evaluate the safety and efficacy of novel therapeutic agents in hospitalized adults diagnosed with COVID-19. The study is a multicenter trial that will be conducted in up to approximately 100 sites globally. The study will compare different investigational therapeutic agents to a control arm. There will be interim monitoring to allow early stopping for futility, efficacy, or safety. If one therapy

proves to be efficacious, then this treatment may become the control arm for comparison(s) with new experimental treatment(s). Any such change would be accompanied by an updated sample size. Because background standards of supportive care may evolve/improve over time as more is learned about successful management of COVID-19, comparisons of safety and efficacy will be based on data from concurrently randomized subjects. An independent Data and Safety Monitoring Board (DSMB) will actively monitor interim data to make recommendations about early study closure or changes to study arms.

The initial sample size is projected to be 572 subjects to achieve 400 subjects with a “recovered” status (per the primary objective). The primary analysis will be based on those subjects enrolled in order to 400 recoveries. An additional analysis of the moderate severity subgroup (those with baseline status of “Hospitalized, requiring supplemental oxygen” or “Hospitalized, not requiring supplemental oxygen - requiring ongoing medical care”) is also of public health importance. Hence, enrollment will be permitted until the date of April 20, 2020 to ensure 400 recoveries and provide additional data about this important subgroup. With recent enrollment rates, the total sample size may be 600 to over 800.

If any additional therapeutic arms are added, the sample size will be recalculated.

Subjects will be assessed daily while hospitalized. If the subjects are discharged from the hospital, they will have a study visit at Days 15, 22, and 29. For discharged subjects, it is preferred that the Day 15 and 29 visits are in person to obtain safety laboratory tests and OP swab and blood (serum only) samples for secondary research as well as clinical outcome data. However, infection control or other restrictions may limit the ability of the subject to return to the clinic. In this case, these visits may be conducted by phone, and only clinical data will be obtained. The Day 22 visit does not have laboratory tests or collection of samples and may also be conducted by phone.

The primary outcome is time to recovery by Day 29 (see table below for definition based on the ordinal scale). A key secondary outcome evaluates treatment-related improvements in the 8-point ordinal scale at Day 15. As little is known about the clinical course of COVID-19, an evaluation of the pooled (i.e., blinded to treatment assignment) proportion recovered will be used to gauge whether the targeted total number of subjects in the recovered categories of the ordinal scale will be achieved with a planned sample size of 572. The primary analysis will include data from both severity groups using a stratified log-rank test. The analysis of the pilot data will be blinded, allowing for the pilot data to be included in subsequent analyses.

The study will randomize subjects 1:1 to placebo or investigational product. In the absence of an established treatment, the use of placebo is justified. If additional arms are added to or dropped from the trial, randomization will proceed with an equal probability of assignment to each of the remaining arms. Randomization will be stratified by site and severity (severe versus mild-moderate). See Section 6.3 for more information on randomization and stratification.

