9.4.2 Analysis of the Primary Efficacy Endpoint

The primary efficacy analysis is a stratified log-rank test, where stratification is according to baseline disease severity (i.e. protocol defined mild/moderate vs severe disease). Deaths will be considered censored at Day 29.

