4.2.3. Method of Assigning Subjects to Treatment Groups (Randomization)

Enrollment and randomization of subjects is done online using the enrollment module of Advantage eClinical[®].

Eligible subjects will be randomized and assigned in a 1:1 ratio to either remdesivir or placebo, with stratification by site and disease severity (Mild/Moderate disease or Severe disease). The randomization is based on a variable blocked scheme to provide an approximately balanced allocation to the treatment groups during the study. If arms are added or removed later in the study, randomization will continue in an equal allocation manner.

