6.7. Multicenter Studies

Data will be pooled across all clinical sites. Secondary analyses of the primary outcome will account for site via stratification by geographic region as noted in Section 6.4.

A sensitivity analysis of the primary outcome will be performed to assess the impact of individual sites on the observed treatment effect. Letting M be the total number of sites, the primary analysis will be repeated by excluding a single clinical site and performing the analyses on the remaining $M-1$ sites. This process will be repeated so that estimates are generated for each of the $M-1$ subset datasets. Presentations from these analyses are described in Section 8.1.2.

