8. EFFICACY EVALUATION

8.1. Primary Efficacy Analysis

8.1.1. Primary Analyses

All the summaries described in this section will be generated for both the early and the full analysis sets.

The primary analysis uses the stratified log rank test to compare treatment to control through Day 29 with respect to time to recovery, as defined in Section 3.3. Stratification is based on mild/moderate versus severe disease at baseline. As noted in Section 3.3, all deaths within 29 days will be considered censored at Day 29 with respect to time to recovery. Conceptually, a death corresponds to an infinite time to recovery, but censoring at any time greater than or equal to Day 29 gives the same answer as censoring at Day 29; both correspond to giving deaths the worst rank.

Let MM and S denote the Mild/Moderate and Severe subgroups, respectively. The z-score associated with the stratified log rank test is

$$Z = \frac{\sum_{MM}(O_i - E_i) + \sum_S(O_i - E_i)}{\sqrt{\sum_{MM} V_i + \sum_S V_i}}$$

The sums are over recovery times t_i in the mild/moderate and severe subgroups, O_i is the number of treatment arm participants recovering at time t_i , and E_i and V_i are the null expected value and variance of the number of treatment recoveries calculated using the hypergeometric distribution. Specifically, if n_{Ti} and n_{Ci} denote the numbers of patients 'at risk' in the two arms in a given stratum at t_i , and r_i is the total number of recoveries at t_i , then $E_i = r_i n_{Ti} / (n_{Ti} + n_{Ci})$ and $V_i = r_i (n_i - r_i) n_{Ti} n_{Ci} / [n_i^2 (n_i - 1)]$, where $n_i = n_{Ti} + n_{Ci}$. The O_i , E_i , and V_i are computed separately within the mild/moderate and severe strata.

As noted in Section 6.6.2, to maintain an overall two-sided type-I error rate of 0.05, the Lan-DeMets spending function analog of the O'Brien-Fleming boundary will be used to derive the cumulative error spending and boundaries for the interim analyses.

The log rank test will be performed using the pseudocode provided in Section 6.1. The following pseudocode can be used to compute the bounds for the final analyses and compare to the calculated log-rank statistic. The `Boundaries` dataset will contain the updated boundaries calculated from the interim analyses using the actual information levels observed at the interim analyses.

```
data Parms_LogR;
  set logrankp(rename=(Statistic=Estimate));
  if Variable='TreatmentVariable';
  _Scale_='Score';
  _Stage_= AnalysisNumber;

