8.1.2. Supplemental and Sensitivity Analyses

For all supplemental and sensitivity analyses of the primary outcome, p-values will not be reported, and 95% confidence levels will be used for confidence interval estimates.

The primary analysis will be repeated in the Treated analysis population where subjects who are ineligible at baseline will be censored at enrollment. The tabular and graphical summaries described in the previous section will be replicated for this Treated analysis.

Sensitivity analyses will be performed using Cox proportional hazards models to estimate the hazard ratio. First, an ITT analysis will be performed in which subjects who die prior to recovering are treated as experiencing a competing risk in the Fine-Gray proportional hazards regression model. Second, a Cox model will be fit with binary indicators for treatment group and disease severity (Mild/Moderate vs. Severe [separate models for randomized stratum and actual stratum]) as well as a treatment * disease severity interaction term. The models will be fit to the ITT analysis population. The treatment group hazard ratios and CIs will be reported for both sets of models and the interaction term p-value will be reported for the interaction models.

The primary analysis will also be repeated using the other subgroups defined in Section 6.4 in place of disease severity. Each subgroup will be considered separately and the tabular and graphical summaries described in the previous section will be replicated for each subgroup. The tabular summary will also include results from an analysis of time to recovery controlling for age and duration of symptoms as continuous covariates. A forest plot will be generated to display the overall treatment hazard ratio estimate and CI from each of the within-stratum analyses (Figure 6). These analyses will be performed in the ITT and Treated populations.

In addition, a forest plot will be generated for the “leave one out” sensitivity analyses described in Section 6.7; hazard ratio estimates and CIs will be provided for each subgroup that leaves a single site out.

An additional sensitivity analysis will evaluate the effect of recoveries that were not sustained as indicated in Section 3.3.2.

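### The region analysis meant to account for site drops severity, so no planned overall recovery hazard ratio keeps severity and adds region

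*Protocol*

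**What the plan says.** **Randomization.** Protocol 4.1: "Randomization will be stratified by site and severity (severe versus mild-moderate"). Protocol 6.3 lists the same two factors, and SAP 4.2.3 has allocation "with stratification by site and disease severity (Mild/Moderate disease or Severe disease").

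**Primary test.** Protocol 9.4.2: "The primary efficacy analysis is a stratified log-rank test, where stratification is according to baseline disease severity". SAP 8.1.1 agrees: "Stratification is based on mild/moderate versus severe disease at baseline". Site is not in the test.

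**How site is to be handled.** SAP 6.7 pools the sites and then states: "Secondary analyses of the primary outcome will account for site via stratification by geographic region as noted in Section 6.4". It adds a leave-one-site-out analysis, in which "the primary analysis will be repeated by excluding a single clinical site and performing the analyses on the remaining" sites.

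**How the region analysis is run.** SAP 8.1.2: "The primary analysis will also be repeated using the other subgroups defined in Section 6.4 in place of disease severity". Each factor is taken separately. SAP 6.4 offers two region groupings (US against non-US; North America, Asia, Europe), and 6.7 does not say which one stands in for site.

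**What is tabulated.** In the Table 14 shell, the row covering all severities carries the stratified Cox hazard ratio. The programming notes for Tables 16 and 17, which hold the subgroup versions, tell the programmer to leave that kind of row out.

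**The concern.** SAP 6.7 promises an analysis of recovery that accounts for site. As specified in 8.1.2, it brings in region, a coarse grouping of the site strata, by removing severity, the other randomization factor and the one the primary test relies on. The result cannot be read cleanly beside the primary hazard ratio, because two things change at once. Dropping a prognostic factor also pulls a hazard ratio toward 1, even when the arms are balanced on it.

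Region could plausibly matter. Recovery includes discharge, and Protocol 6.5 lets background COVID-19 drugs follow written local policy. One mitigation is that patients kept in hospital only for infection control already count as recovered (Protocol 8.1.2.2). What is at stake is the usefulness of one supportive estimate, not the validity of the trial's main test.

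**Working it through.** **1. Inventory of the recovery analyses.**

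| Analysis (SAP) | Severity kept? | Site or region in the model? |
|---|---|---|
| Primary log-rank and Cox (8.1.1) | yes | no |
| Fine-Gray (8.1.2) | not stated | no |
| Severity interaction model (8.1.2) | yes | no |
| Age and symptom duration as covariates (8.1.2) | not stated | no |
| Region in place of severity (6.7, 8.1.2) | no | region |
| Leave one site out (6.7) | yes | no; one site removed at a time |

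No row has severity together with site or region. SAP 8.1.2 closes by allowing additional analyses, without specifying any. The text of 8.1.2 would repeat the 8.1.1 summaries for each factor, which include an overall ratio, while the Table 16/17 notes omit it. Even if it were shown, it would not contain severity.

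**2. The plan's own figure.** Protocol 9.2: E = 4(1.96 + z_β)² / (ln θ)². With θ = 1.35 and z_β = 1.036, E = 4 × 8.98 / 0.0901 ≈ 399, against 400 stated. 400 / 0.70 = 571.4, so 572. Both reproduce, and this point does not affect them.

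**3. Size.** I simulated the SAP 8.1.1 statistic, Z = Σ(O−E)/√ΣV, taking exp{Σ(O−E)/ΣV} as the approximate hazard ratio.

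- From the documents: N = 572, about 70% recovered, ratio 1.35, 1:1 allocation, 28 days.
- Assumed, because the documents give no figures: 60 or 100 sites of equal or skewed size; three regions (80/15/5%); 85% severe; severe-to-mild recovery rate ratio 0.4; blocks of 2 and 4 within site by severity; site/region standard deviations on the log-rate scale as in the table.
- 1,500 runs per setting; Monte Carlo error about 1 point for power. Ranges are over the four site layouts.

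| Site/region SD | Power: severity only | Power: region only (as planned) | Power: both | Ratio: region only | Ratio: both |
|---|---|---|---|---|---|
| 0 / 0 | 83.3–86.0% | 80.5–82.2% | 82.7–85.7% | 1.336–1.341 | 1.356–1.364 |
| 0.3 / 0.2 | 81.5–83.2% | 79.1–80.9% | 82.3–83.3% | 1.321–1.331 | 1.340–1.351 |
| 0.6 / 0.3 | 74.1–75.7% | 71.8–74.7% | 74.3–76.5% | 1.292–1.303 | 1.305–1.317 |

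Within settings, both factors against region alone gain 1.2 to 3.5 points, and the ratio rises by 0.013 to 0.025. Both factors against severity alone range from −0.6 to +0.8 points.

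**4. Where the difference comes from.** It is attenuation, not interval width. In the first setting (60 equal sites, no site or region effect), ΣV is 94.9 for region alone and 93.1 for both, so the standard errors of the log ratio are 1/√94.9 = 0.103 and 1/√93.1 = 0.104. Expected Z is ln(1.336) × √94.9 = 2.82 against ln(1.356) × √93.1 = 2.94. Normal-approximation power is then Φ(0.86) = 81% and Φ(0.98) = 84%, close to the simulated 80.5% and 82.7%.

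**5. Other assumed inputs.** With 60 unequal sites and 12% mild-moderate, one set (2,500 runs, four settings) gave gains over region alone of 2.6, 2.6, 2.3 and 2.9 points. Another (1,200 runs, three settings) gave 2.8, 3.1 and 2.3. Against severity alone, the two sets ranged from −0.3 to +2.2 points, the top value needing a region effect of ±0.6 on the log-rate scale.

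**The case against.** The strongest reply is that nothing reported depends on this. SAP 8.1.2 gives no p-values for supplemental analyses, so points of power describe a test that will not be presented. The forest plot and Tables 16–17 are mainly within-region displays. This stands: the power figures only put the attenuation on a familiar scale.

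A reader might infer that the primary analysis loses precision by ignoring site. The documents do not support that. They give no between-site or between-region variation; without it, omitting site costs nothing. Nor would conditioning on site itself be an obvious gain. With 572 subjects and up to about 100 sites there are 572/200 = 2.9 per site-by-severity cell. In the simulations, full site-by-severity strata gave 6 to 13 points less power than severity alone when sites did not differ, 3 to 12 less at SD 0.3, and between 4 less and 5 more at SD 0.6. Leaving site out of the primary test is defensible.

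A reader might also infer that the region analysis is the only one that addresses site. The leave-one-site-out analysis does so too, with severity kept. It measures the influence of single sites rather than adjusting for them, so the gap in adjustment remains.

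Finally, the proposed analysis conditions on region, not site. That is true, and it is what SAP 6.7 itself chose as the stand-in.

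**Conclusion.** The point holds as a minor gap between what SAP 6.7 promises and what 8.1.2 and the shells deliver: no specified analysis yields an overall recovery hazard ratio that keeps severity and adds region. Under the assumed effects, keeping severity makes that supportive estimate slightly less attenuated, by 0.013 to 0.025 at a true ratio of 1.35. That is equivalent to about 1 to 4 points of power over region alone. The size depends mainly on the assumed severity effect and mix, which the documents do not give.

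The primary severity-stratified test is valid. Any cost there is mild attenuation and conservatism if sites or regions really differ: at SD 0.6/0.3 the severity-only ratio averaged 1.301 to 1.311, with null rejection of about 3 to 4%. It is not a false-positive risk. SAP version 3.0 was written after the interim results had gone to the DSMB and been made public (SAP 2.1), so the ACTT-1 primary test should not be re-stratified.

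**What to change.** Free improvement. In SAP 6.7 and 8.1.2:

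- Stratify the region analysis by severity and region together: North America, Europe and Asia by the two severity strata, with severity classified as in the primary analysis.
- Report the overall stratified Cox hazard ratio and its 95% confidence interval beside the primary hazard ratio, labelled supportive.
- Add that row to the Table 16/17 shell. The within-region rows can stay as planned.

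The cost is one more variable in the strata statement and one table row, with no new data. If region has no effect, the simulated loss against severity alone was 0.2 to 0.6 points of power, within Monte Carlo error. The primary analysis is unchanged.
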